5.6.1 Extent of Exposure

Summaries for exposure will be provided. This consists of a descriptive summary of study medication duration in days. In addition, total study medication duration and time at risk will be

5.6

summarized in years by treatment group. The cumulative study medication duration will be summarized for study participants exposed for given durations of time, with four weekly categories through Week 16: izzation

- >0 week
- >4 weeks
- >8 weeks
- ≥ 12 weeks
- >16 weeks

Definitions for study medication duration (days) during the Treatment Period are provided as follows: s eleo

Study medication duration (days):

- Date of last dose - date of first dose + 28 days

The use of +28 days reflects the dosing interval of Q4W.

Note: For participants who died during the treatment period, the calculation reverts to:

- Date of death – date of first dose + 1

Time at Risk (Days) during the Treatment Period:

For study participants who complete the final visit (week 16) of the Treatment Period:

• Date of Week 16 visit – Date of first dose +1

For study participants who discontinue on or prior to the final visit of the Treatment Period, use the minimum of the following:

- Planned total number of days in the Treatment Period (112 days)
- Date of last clinical contact Date of first dose +1

For study participants who died during the Treatment Period:

Date of death – date of first dose +1

Date of last clinical contact for each study participant in the Treatment Period is defined as the maximum of last visit date in the Treatment Period, last imputed AE start date, date of study termination or completion, last date of study drug administration.

Time at Risk (Days) during the Treatment Period + SFU:

For study participants who complete the final visit (week 16) of the Treatment Period and enter the MAP:

Date of Week 16 visit – Date of first dose +1

For study participants who do not enter the MAP, use the minimum of the following:

- Date of last dose Date of first dose +141
- Date of last clinical contact Date of first dose +1

For study participants who died prior to the end of time at risk as defined above:

Date of death - date of first dose +1

Date of last clinical contact for each study participant in the Treatment Period + SFU is defined as the maximum of: last visit date including SFU, last imputed AE start date, date of study termination or completion, last date of study drug administration.

5.6.2 **Adverse Events**

ion An AE is any untoward medical occurrence in a subject or clinical investigation subject administered a pharmaceutical product that does not necessarily have a causal relationship with this treatment. An AE can therefore be any unfavorable and unintended sign (including an abnormal laboratory finding), symptom, or disease temporally associated with the use of a medicinal (investigational) product, whether or not related to the medicinal (investigational) product. Adverse events will be coded according to the Medical Dictionary for Regulatory Activities (MedDRA version 19.0).

5.6.2.1 **Data considerations**

Treatment-emergent AEs are defined as those AEs that have a start date on or following the first dose of IMP through the to the end of the time at risk, as defined in section 5.6.

The rules for imputing partial start or stop dates are outlined in 5.1.1.7.3. If it is not possible (due to partial dates) to determine whether an AE is treatment-emergent then it will be assumed to be a TEAE. If the intensity of an AE is unknown, it will be considered as severe. If the relationship to study drug is missing, it will be considered as related.

Treatment-emergent AEs will be summarized as study participant incidence (number and percentage of study participants experiencing the AE) and AE frequencies (number of AEs including repeat events) by treatment group.

Selected AE summaries will include the exposure-adjusted incidence rate (EAIR) and the exposure-adjusted event rate (EAER). The 95% CIs will be reported for the EAIR only.

The EAIR is the total number of study participants with a specific AE divided by the total time at risk across all study participants. If a study participant has multiple events, the time of exposure is calculated to the first occurrence of the AE being considered. If a study participant has no events, the total time at risk is used. The EAER is the total number of AEs including repeat occurrences in individual study participants divided by the total time at risk across all study participants. Exposure adjusted rates (EAIR and EAER) will be scaled to 100 participant-years. Study participant time at risk represents the time a participant is at risk for having an AE. These definitions will be used in calculations of exposure-adjusted rates for adverse events.

Details of the calculations for exposure adjusted rates (EAIR and EAER) can be found in section 6.1.5.2

The following PTs will be used to classify COVID-19 adverse events:

- Corona virus infection
- Coronavirus test positive

A separate summary and by-study participant listing will be produced for COVID-19 TEAEs.

To assess the impact of COVID-19 mass vaccination on TEAEs, a sensitivity analysis will present all TEAEs excluding TEAEs assessed as exclusively related to COVID-19 vaccine by the investigator. TEAEs recorded as related to both study medication and COVID-19 vaccination will not be excluded. A complementary table and listing of TEAEs related to COVID-19 vaccine will be presented.

Another sensitivity analysis will present all TEAEs excluding TEAEs with start date on or up to 5 days after date of COVID-19 vaccine. Note that study participants may receive more than one administration of COVID-19 vaccine. A complementary table and listing of TEAEs with start date on or up to 5 days after date of COVID-19 vaccine will also be presented.

5.6.2.2 AE Summaries

The AE summaries listed below will be provided based on incidence during the Treatment Period.

The following summaries will be provided by treatment group. In addition, all summaries of TEAEs based on "100 subject years" will include EAIR (with 95% confidence interval) and EAER.

- Incidence of TEAEs Overview
- Incidence of TEAEs per 100 subject years by SOC, HLT, and PT
- Incidence of Serious TEAEs per 100 subject years by SOC, HLT, and PT
- Incidence of TEAEs Leading to Discontinuation per 100 subject years by SOC, HLT, and PT
- Incidence of TEAEs Leading to Death by SOC, HLT, and PT
- Incidence of TEAEs by Maximum Relationship by SOC, HLT, and PT
- Incidence of COVID-19 TEAEs by SOC, HLT, and PT
- Incidence of TEAEs by during and post COVID-19 pandemic by SOC, HLT, and PT (if applicable, see section 5.2.1)
- Incidence of Related Serious TEAEs by SOC, HLT, and PT
- Incidence of TEAEs by Maximum Intensity, SOC, HLT, and PT
- Incidence of TEAEs by decreasing frequency of PT
- Incidence of Non-Serious TEAEs by SOC, HLT, and PT
- Incidence of Non-Serious TEAEs by Maximum Relationship SOC, HLT, and PT
- Incidence of Non-Serious TEAEs Above Reporting Threshold of 5% by SOC and PT
- Incidence of Serious TEAEs by Relationship SOC and PT
- Incidence of Related TEAEs by SOC, HLT, and PT
- Incidence of TEAEs per 100 subject years by SOC, HLT, and PT and by Time of Onset Relative to Anti-bimekizumab Antibody Status (subjects treated with BKZ)
- Incidence of TEAEs per 100 subject years by SOC, HLT, and PT and by Time of Onset Relative to Neutralizing Anti-bimekizumab Antibody Status (subjects treated with BKZ)

In addition, the AE summaries listed below will be provided based on the incidence in the Treatment + SFU Period.

- Incidence of TEAEs Overview
- Incidence of TEAEs per 100 subject years by SOC, HLT, and PT
- Incidence of Serious TEAEs per 100 subject years by SOC, HLT, and PT
- Incidence of TEAEs Leading to Discontinuation per 100 subject years by SOC, HLT, and PT
- Incidence of TEAEs Leading to Death by SOC, HLT, and PT

A by-study participant listing of TEAEs which code to the "Infections and Infestations" SOC and Emerged within 30 days of when a CTCAE Grade 3 or 4 Neutrophil Value Occurred will be presented.

The AE summaries listed below will be provided to assess the impact of COVID-19 mass vaccination on TEAEs through the Treatment Period.

- Incidence of TEAEs Excluding TEAEs Exclusively Related to COVID-19 Vaccine by SOC, HLT, and PT (all SS)
- Incidence of TEAEs Exclusively Related to COVID-19 Vaccine by SOC, HLT, and PT (all participants in the SS who received at least one COVID-19 vaccine during the study)
- Incidence of COVID-19 Vaccine Interval Censored TEAEs by SOC, HLT, and PT (all SS)
- Incidence of COVID-19 Vaccine Interval TEAEs by SOC, HLT, and PT (all participants in the SS who received at least one COVID-19 vaccine during the study)

A by-study participant listing of TEAEs related to COVID-19 vaccine and a listing of COVID-19 vaccine interval TEAEs will be presented.

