- ^b The Screening Period will last 2 weeks, but can be extended up to a total of 5 weeks in cases where a laboratory assessment needs to be repeated or to allow washout of prohibited medications.
- ^c For study participants not entering the MAP, the SFU Visit will occur 20 weeks after the final dose of IMP. No SFU will occur for study participants entering the MAP.
- ^d Ensure no significant changes in medical history.
- ^e Includes evaluation of signs and symptoms of active TB and risk for exposure to TB.
- ^f The physical examination will be performed as per protocol.
- ^g Vital signs (sitting systolic and diastolic blood pressure, pulse rate, and body temperature) are to be measured prior to blood sampling, and prior to IMP dosing, where applicable.
- ^h Pregnancy testing will consist of serum testing at Screening. A urine pregnancy test will be administered at all other visits.
- ⁱ Study participants who have evidence of or test positive for hepatitis B by any of the following criteria: 1) HBsAg+; 2) HBcAb+ are excluded. A positive test for HCV is defined as: 1) positive for hepatitis C antibody (anti-HCV Ab), and 2) positive via a confirmatory test for HCV (for example, HCV polymerase chain reaction) are also excluded. Study participants will also be tested for antihepatitis B surface antibody.
- ^j The HIV test results will not be recorded in the eCRF.
- ^k Screening chest x-ray must occur within 3 months prior to the Screening Visit.
- ^l Tuberculosis questionnaire will be required at PEOT.
- ^m The scalp IGA will only be assessed for those study participants with scalp involvement (scalp IGA score >0) at Baseline.
- ⁿ IMP administration is based on randomization.
- ^o The dosing window is ± 3 days relative to the scheduled dosing visit through Week 16.
- ^p Samples will be collected prior to any IMP dosing at a visit.
- ^q If an Unscheduled Visit is conducted due to safety or efficacy reasons, a C-SSRS assessment will be performed with the subject during the visit. If an Unscheduled Visit is conducted for reasons other than safety or efficacy concerns (eg, repeated collection of a laboratory specimen due to collection or analysis issues), a C-SSRS will not be required at these visits.

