6.8 Treatment after the end of the study

Study participants who have completed the 16-week Treatment Period may choose to enter into a MAP to receive open-label treatment with bimekizumab or enter the SFU.

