1.2 Study design

This is a Phase 3, multicenter, randomized, double-blind, placebo-controlled, parallel group study to evaluate the efficacy and safety of bimekizumab compared with placebo in adult Korean study participants with moderate to severe plaque PSO. The aim of this study is to bridge the existing evidence of efficacy and safety of bimekizumab from the Phase 3 program with limited

Korean study participation to a Korean population of study participants with moderate to severe PSO.

The study population consists of adult Korean study participants (>19 years of age) with a diagnosis of moderate to severe plaque PSO (Baseline PASI ≥12 and BSA affected by PSO \geq 10% and IGA score \geq 3 on a 5-point scale) who are candidates for systemic PSO therapy and/or phototherapy. authorizat authorizat phototherapy.

This study will include 3 periods [Figure 1]:

- Screening Period (2 to 5 weeks) •
- Treatment Period (16 weeks) •
- Safety Follow-Up (SFU) Period (20 weeks after the last dose of IMP)

One rescreening may be allowed after consultation with the Medical Monitor

After completion of the Screening Period, eligible study participants will be allowed to enroll into the study. Approximately 45 adult Korean study participants will be randomized 2:1 to receive the following blinded IMP regimens during the Treatment Period:

- Bimekizumab 320mg every 4 weeks (Q4W) administered subcutaneous (sc) injection (30 • study participants)
- Placebo Q4W administered sc injection (15 study participants)

During the Treatment Period, IMP will be administered at the study site.

Study participants who have completed the 16-week Treatment Period may choose to enter into a Managed Access Program (MAP) to receive open-label treatment with bimekizumab or enter the SFU.

All study participants choosing not to transition into a MAP will have a SFU Visit 20 weeks post last dose of IMP. Safety assessments will be made by ongoing monitoring and evaluation of AEs and other safety topics of interest specific to bimekizumab.

Study participants withdrawing early from IMP will undergo the premature end of treatment (PEOT) Visit assessments and be asked to continue in the SFU Period.

A study participant is considered to have completed the study if he/she has completed the 16 this document cation week treatment period, regardless of entry into the MAP or completion of the SFU period.

Figure 1 Study schematic

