#### Treatment Compliance 6.1.10

Study treatment compliance will be calculated and summarized for the SS.

Treatment compliance will be calculated as:

(Actual number of completed injections/Expected number of injections)  $\times$  100

In this study, Baseline visit and Weeks 4, 8, 12 are dosing visits. For study participants who complete all injections as planned, the expected number of injections is 8. For participants who permanently discontinue treatment, the number of expected injections is based on the time of early discontinuation relative to the dosing visits.

Bimekizumab

Compliance will be summarized descriptively by treatment group and overall. The number and percentage of study participants meeting certain compliance thresholds (<75% and  $\geq 75\%$ ) will also be reported.

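### Crude percentages in the Treatment + SFU adverse-event tables mix about 16 and about 32 weeks of follow-up, so they depend on each arm's uptake of the managed access program

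*SAP*

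**What the plan says.** SAP 5.6.2.2 plans two sets of adverse-event tables. The main set is introduced by "The AE summaries listed below will be provided based on incidence during the Treatment Period". A second set of five follows: "In addition, the AE summaries listed below will be provided based on the incidence in the Treatment + SFU Period". The five are the TEAE overview, all TEAEs, serious TEAEs, TEAEs leading to discontinuation, and TEAEs leading to death. The middle three are labelled per 100 subject years, so they carry an exposure-adjusted incidence rate (EAIR, with 95% CI) and event rate (EAER). The overview and death tables are not so labelled.

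Who is followed after Week 16 is settled by the participant. Protocol 6.8 offers completers two routes: open-label bimekizumab under the MAP, or SFU. The footnotes to the protocol's schedule of activities add: "No SFU will occur for study participants entering the MAP". For everyone else, SAP 1.2 says: "All study participants choosing not to transition into a MAP will have a SFU Visit 20 weeks post" last dose.

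SAP 5.6.1 sets time at risk for the combined window accordingly. The rule that begins "For study participants who complete the final visit (week 16) of the Treatment Period and enter" the MAP stops the clock at the Week 16 visit. The other rule begins "For study participants who do not enter the MAP, use the minimum of the following" and takes the earlier of last dose plus 20 weeks and last clinical contact.

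The section on study periods (SAP 5.1.1.1.3) says that SFU data are otherwise only listed. The exceptions are the ALT/AST figures and the adverse-event summaries of 5.6.2.2.

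**The concern.** A crude percentage with an event has no time in it. When some participants are observed about twice as long as others, it rises with the share observed longer. Here that share is set by a choice made after randomization, and nothing in the plan makes it equal between arms. The sample-size section assumes very different response in the two arms (70% vs 13.3% PASI90), so equal uptake cannot be presumed, although the documents give neither an uptake figure nor a direction.

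The secondary safety endpoints are incidences over the whole study, and the combined window is the closest match to that wording. A reader who takes its percentages as the safety comparison could see a difference that comes only from MAP uptake. Because these pooled tables are also the only tabulation of SFU adverse events, SFU incidence among the people actually followed there cannot be read from any planned table.

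**Working it through.** **Follow-up per participant.** The plan gives no figure for this effect, but its time-at-risk rules can be evaluated. The constant 141 in SAP 5.6.1 is 20 × 7 + 1. On dosing, SAP 6.1.10 says: "In this study, Baseline visit and Weeks 4, 8, 12 are dosing visits". The last dose is therefore nominally 84 days after the first.

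- MAP entrant: 112 + 1 = 113 days (16.1 weeks).
- Non-MAP completer: 84 + 141 = 225 days (32.1 weeks).
- Ratio: 225 / 113 = 1.99. The extra time is 225 − 113 = 112 days.
- MAP entry requires completing 16 weeks, so early discontinuers fall in the non-MAP group. With one dose only, the cap is 0 + 141 = 141 days.

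**Crude percentage.** Let P be the TEAE risk by Week 16, m the MAP uptake in an arm, and k the hazard after Week 16 relative to the hazard on treatment. All participants are taken as completers, and true risk is the same in both arms.

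- Risk in a MAP entrant: P.
- Risk in a non-MAP participant: Q = 1 − (1 − P)^(1 + k·112/113).
- Percentage in the arm: m·P + (1 − m)·Q.
- Artefact between arms: (difference in m) × (Q − P).

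With P = 50% and k = 1, Q = 1 − 0.5^1.991 = 74.8%. At 90% uptake the percentage is 0.9 × 50 + 0.1 × 74.8 = 52.5%. At 50% uptake it is 0.5 × 50 + 0.5 × 74.8 = 62.4%. The artefact is 9.9 points. Uptake, P and k are assumptions, so the range matters (k = 1, artefact in points):

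| MAP uptake | P = 10% | P = 30% | P = 50% | P = 60% |
|---|---|---|---|---|
| 90% vs 50% | 3.6 | 8.3 | 9.9 | 9.5 |
| 80% vs 60% | 1.8 | 4.2 | 5.0 | 4.8 |
| equal | 0 | 0 | 0 | 0 |

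**Exposure-adjusted rates.** EAER is expected events over expected time at risk. With on-treatment hazard h, EAER = h·(113 + k(1 − m)·112) / (113 + (1 − m)·112). When k = 1 the bracket cancels and EAER = h at any uptake. EAIR, which cuts time at the first event, also returns h. For P = 50% both are 224.0 per 100 participant-years in both arms.

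A simulation at 30 vs 15 participants (40,000 replicates, 90% vs 50% uptake, k = 1) agrees. Mean percentages are 52.6% vs 62.5%, mean EAER 224.1 vs 223.9 and median EAIR 224.7 vs 225.7. Mean EAIR is 229.4 vs 235.6. That difference is small-sample bias from arm size: an arm of 15 at 90% uptake also gives 234.3.

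If the hazard changes after Week 16, the rates do move. At P = 50% and 90% vs 50% uptake:

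| k | Percentages | EAIR (ratio) | EAER (ratio) |
|---|---|---|---|
| 0.5 | 51.5 vs 57.3 | 217.9 vs 198.8 (1.10) | 213.9 vs 186.9 (1.14) |
| 1 | 52.5 vs 62.4 | 224.0 vs 224.0 (1.00) | 224.0 vs 224.0 (1.00) |
| 2 | 53.7 vs 68.7 | 232.1 vs 259.3 (0.90) | 244.2 vs 298.3 (0.82) |

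So the percentage is always higher in the arm with more SFU follow-up, while the rate artefact changes sign with k.

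**The case against.** The plan already contains most of what a careful reader needs. All five tables are also produced for the Treatment Period alone, where completers share one window and the artefact is zero. The three secondary safety endpoints match the three pooled tables that carry EAIR and EAER. SAP 5.6.1 summarizes time at risk by treatment group, and SAP 5.2 reports how many complete SFU and how many enter the MAP. No adverse-event test is planned. The size also rests on assumed uptake. At 30 vs 15 participants, one placebo participant is 1/15 = 6.7 points, and the standard error of a difference near 50% is √(0.25/30 + 0.25/15) = 15.8 points, so an artefact of 5 to 10 points lies within sampling noise.

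Most of this stands, and it makes the point modest. Two things remain. The SAP does not say which set of tables is the between-arm comparison. And no planned table gives SFU incidence. Subtracting participant counts between the two sets yields only people whose first event fell in SFU, not all with an SFU event.

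A reader might go further and infer that the exposure-adjusted rates are also shifted by construction, or that the arm with more SFU follow-up must show a lower rate. The documents do not support either. EAIR and EAER use each participant's own time at risk, with separate MAP and non-MAP rules, and are unaffected by uptake under a constant hazard. They shift only if the hazard changes after Week 16 or MAP entry is related to adverse-event risk. The plan gives no figure for either, and the direction depends on which applies.

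**Conclusion.** The point holds for crude percentages in the Treatment + SFU tables. They combine 113-day and 225-day follow-up, so unequal MAP uptake produces a between-arm difference without any difference in risk. Under a constant hazard, with 16-week risks of 10% to 60%, the artefact is 3.6 to 9.9 points at 90% vs 50% uptake and 1.8 to 5.0 points at 80% vs 60%. It is zero at equal uptake. The uptake, risk and hazard values are assumptions; only the two follow-up lengths come from the plan. For EAIR and EAER the effect is conditional, not structural. The Treatment Period tables are sound for comparing arms. This is a worthwhile improvement to reporting and does not threaten the trial's safety conclusions.

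**What to change.** In SAP 5.6.2.2:

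- State that the Treatment Period tables are the between-arm comparison.
- Add a descriptive SFU-only adverse-event table by arm, running from the day after the Treatment Period ends to the end of time at risk. Use participants who entered SFU as the denominator and their SFU time as exposure. Label it as a self-selected group and not a randomized comparison.
- In the pooled Treatment + SFU tables, show the number per arm with SFU follow-up, add EAIR and EAER to the Overview, and footnote that crude percentages reflect unequal follow-up.

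The cost is SAP wording and a few extra tables from data already collected. The drawback is small SFU denominators: with 20% of an arm entering SFU, 0.2 × 15 = 3 or 0.2 × 30 = 6 participants. The SFU table can therefore describe but not compare.

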5.6.2.3 Other safety topics of interest

The following are AEs of other safety topics of interest that require special statistical analyses.

The AE summaries described below will be provided based on incidence in the Treatment Period.

A by-study participant listing of all AEs of safety topics of interest will be presented by type of safety topics of interest.

5.6.2.3.1 Infections (serious, opportunistic, fungal and TB)

Serious infections will be identified based on MedDRA classification (SOC "Infections and infestations") using the "Any SAE" table. A separate table does not need to be produced to summarize these events.

Fungal infections will be summarized in a stand-alone table. The table will include all TEAEs (serious and non-serious) which code into the High Level Group Term "Fungal infectious disorders"

Opportunistic infections (including tuberculosis [TB]) will be summarized in a stand-alone table. The table will include all opportunistic infection TEAEs identified using UCB-defined search criteria which were adjudicated as opportunistic infections.

